6 ENDPOINTS AND COVARIATES

6.1 SAFETY ENDPOINTS

- All Adverse Events (AEs) Occurrence

6.2 EFFICACY/ EFFECTIVENESS ENDPOINT(S)

- *Cumulative percent of patients who become pregnant over the 6 month observation period*
- *Rate of pregnancies per 100 person-years of follow-up*
- *The patient response to endometriosis pain treatment*

7 HANDLING OF MISSING VALUES

No imputation of missing data will be performed. Missing or incomplete data will be excluded from the analyses.

8 STATISTICAL METHODOLOGY AND STATISTICAL ANALYSES

8.1 STATISTICAL METHODS

8.1.1 Analysis for Continuous Data

Descriptive summary statistics for continuous variables will include the following:

- number of subjects (n), mean, median, SD, minimum and maximum.

No formal statistical analyses will be performed on continuous data.

8.1.2 Analysis for Categorical Data

Descriptive statistics for categorical variables will be given as frequencies and percentages. Unless specified otherwise, the denominator will be the number of subjects included in the safety analysis set or the efficacy analysis set depending on what analysis is presented. Where appropriate, percentages will be presented with a corresponding 95% confidence interval. Comparisons between subcategories of each baseline characteristic will be made using a chi-square test or Fisher's exact test as appropriate. When more than 20% of expected frequency of the cell count is less than 5, Fisher's exact test will be used instead of the chi-square test.

8.2 STATISTICAL ANALYSES

8.2.1 Safety Analysis

[figure not shown]
[figure not shown]
Total number of participating institutions, enrolled and retrieved cases, and the number of cases included in the analysis will be presented as summary tables.

8.2.1.1 Baseline Characteristics

Baseline characteristics for this study are defined as follows:

- Age[†] (≤ 19 years, ≥ 20 years and ≤ 29 years, ≥ 30 years and ≤ 39 years, ≥ 40 years and ≤ 49 years, ≥ 50 years and ≤ 59 years, ≥ 60 years and ≤ 69 years, ≥ 70 years)
- Weight
- Height
- Purpose of administration (Prevention of pregnancy in women of child bearing potential, Management of endometriosis associated pain)
- Medical history (Past, Present / Yes, No)
- Concomitant medication (Yes, No)
- Concomitant therapy (Yes, No)
- Total number of injections of Sayana[®] (1, 2, 3, 4, >4)
- Dose per injections of Sayana[®] (1 pre-filled syringe(2.25ml), Other)
- Paediatric status (<19 years, ≥ 19 years)

PFIZER CONFIDENTIAL

- Geriatric status (<65 years, \geq 65 years)
- Kidney disorder (Yes, No)
- Liver disorder (Yes, No)

† Age = Using the information recorded in CRFs

8.2.1.2 Adverse Events

All adverse events reported after the start of administration of Sayana® will be considered as on-treatment and summarised. Adverse events reported with partial dates of onset will be assumed as on-treatment, unless the month and year of the AE onset date is before the start date of Sayana®.

In the safety analysis set, the number of subjects to whom AE occurred and the number of AEs will be calculated and the incidence rate of AEs will be estimated with its 95% confidence interval.

8.2.1.3 Adverse Events by Baseline Characteristics

The following will be presented for AEs, split by the baseline characteristics using the safety analysis set:

[figure not shown]
- The number of subjects to whom AE occurred and the number of AEs will be calculated.
- The proportion of subjects to whom AE occurred and its 95% confidence interval will be estimated and compared between subcategories of each baseline characteristic using a chi-square test or Fisher's exact test. When more than 20% of the expected frequency of the cell count is less than 5, Fisher's exact test will be used instead of the chi-square test.
- Adverse event presentations will be split by the following baseline characteristics: age, purpose of administration, medical history (past/present), concomitant medication, concomitant therapy, total number of injections of Sayana®, dose per injections of Sayana®, paediatric status, geriatric status, kidney disorder, liver disorder (see section 8.2.1.1).

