### 7.3.1.4. Concomitant Medication/Therapy

The investigator records the medication/therapy which has been administered/conducted continuously at the point of being enrolled in this study or administered/conducted newly after being enrolled. Check either 'yes' or 'no'. If 'yes', record in detail.

- Name of drug/Therapy name: Record generic name in case of single product and record trade name in case of combination product. Also, record name of concomitant therapy.
- Daily total dosage/Frequency: Record the daily total dosage as unit. If not combination drug, avoid recording in tablets, capsules or vials. Record the frequency of concomitant therapy.
- Duration of administration/Duration of therapy: Record the starting/ending date of the medicated drug and concomitant therapy (year/month/day). If the medication and therapy are being continued at the completion of the study, record the starting date date and check in the box next to 'Ongoing'.
- Purpose of administration/Purpose for therapy: Record the purpose of administration or therapy.

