#### 7.7.1.2. Safety Parameters

Safety parameters include:

[figure not shown]
- Adverse events and serious adverse events;
- Premature discontinuations from the study due to adverse events;
- Use of concomitant medications due to adverse events;
- Clinically significant abnormalities from laboratory test.

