3 INTERIM ANALYSES

As required by MFDS regulations, the periodic report should be submitted to MFDS every 6 months for the first two years and then annual report should be submitted to MFDS for the third, fourth and fifth year. The final report should be submitted in the sixth year. Interim analysis will be performed in time for the report submission.

[figure not shown]
However, according to re-examination period extension, additional annual reports will be submitted to MFDS in the sixth and seventh year and the final report will be submitted in the eighth year.

This Statistical Analysis Plan (SAP) details the analyses and outputs to be produced for the interim and final analyses.

The analyses for types of medical history(past/present disease), types of concomitant medications, any clinically significant abnormal finding from laboratory test reported as an AE (if necessary and data are applicable), the classification of AE by preferred term according to severity, action, seriousness, outcome, causal relationship to Sayana® and other causal relationship regarding occurred AE and estimation of 95% confidence interval for AEs by baseline characteristics, System Organ Classes and Preferred Term of Serious AE/Serious ADR, unexpected AE/ unexpected ADR according to the frequency of AEs in the prescribing information, Basic Results Tables will be performed for the re-examination report (i.e. final report) only.

Note: Although it was planned that interim analyses would be performed for the report submission to the MFDS annually, interim analyses were not performed for the annual reports for the first one year. The first interim analysis will be performed once this SAP is finalized.

PFIZER CONFIDENTIAL

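### Adverse event rates are tested across a "baseline" concomitant treatment flag that can be set by treating the adverse event itself

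*SAP*

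**What the plan says.** SAP 8.2.1.1 lists "Concomitant medication (Yes, No") and the matching item for concomitant therapy among the baseline characteristics, with no date limit. SAP 8.2.1.3 names "concomitant medication, concomitant therapy, total number of injections of Sayana" among the splits for AE tables. It says the proportion of subjects with an AE will be "compared between subcategories of each baseline characteristic using a chi-square test", with Fisher's exact test when expected counts are small. SAP Appendix 1 sets the significance level at two-sided 5%. SAP section 3 lists "estimation of 95% confidence interval for AEs by baseline characteristics" among the analyses for the re-examination report.

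Protocol 7.3.1.4 defines what the field holds: treatment "administered/conducted continuously at the point of being enrolled in this study or administered/conducted newly after being enrolled". For each entry the site must "Record the starting/ending date of the medicated drug and concomitant therapy (year/month/day") and "Record the purpose of administration or therapy". The variables table in Protocol 7.3 gives concomitant medication a baseline role but refers to section 7.3.1 for its definition. Protocol 7.2 still collects concomitant medication at the follow-up call, together with AEs. Protocol 7.7.1.2 lists "Use of concomitant medications due to adverse events" as a safety parameter.

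**The concern.** A characteristic used to compare AE risk should be fixed before the AE can occur. These two flags are not. A woman taking nothing at enrolment who has an AE and is given a drug for it is recorded as a concomitant medication user, so her AE moves her from No to Yes. An untreated woman with no AE has no such route. This mechanism pushes in one direction only, towards more AEs among users, and a larger sample does not remove it.

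A significant result could be read in the re-examination report as a drug interaction or a risk group when it shows only that some AEs were treated.

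A secondary point concerns the total number of injections in the same list, which is also known only after follow-up. Stopping because of an AE, or leaving early, can lower the count, so that split is affected too. Its bias can go either way and is not quantified here.

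**Working it through.** The plan gives no power or error-rate figure for these comparisons, so there is none to reproduce. The question is how often the planned test would be significant if treatment in use at enrolment had no association with AEs.

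**Inputs from the documents**
- n = 600, the minimum in Protocol 7.5.
- Chi-square or Fisher's exact test, two-sided 5% (SAP 8.2.1.3 and Appendix 1).

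**Assumed inputs (not in the documents)**
- a, proportion of women with an AE: 5–30%.
- c, proportion using medication at enrolment: 20–40%.
- t, share of women with an AE, not already users, who are given a drug for it: 10–50%.

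**Formulas** (a and c independent)
- P(Yes) = c + (1 − c)·a·t
- P(AE | Yes) = [c·a + (1 − c)·a·t] / P(Yes)
- P(AE | No) = (1 − c)·a·(1 − t) / [1 − P(Yes)]
- Noncentrality λ = n·P(Yes)·[1 − P(Yes)]·[P(AE | Yes) − P(AE | No)]² / [a(1 − a)]. The rejection probability comes from the noncentral chi-square with 1 df.

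**One case in full: a = 20%, c = 40%, t = 20%**
- P(Yes) = 0.40 + 0.60 × 0.20 × 0.20 = 0.424
- P(AE | Yes) = (0.080 + 0.024) / 0.424 = 24.5%
- P(AE | No) = 0.60 × 0.20 × 0.80 / 0.576 = 16.7%
- λ = 600 × 0.424 × 0.576 × 0.0786² / 0.16 = 5.66, giving a rejection probability of 66%

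**Same a and c, varying t (n = 600)**

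| Share of AEs treated | AE in Yes | AE in No | λ | P(significant) |
|---|---|---|---|---|
| 10% | 22.3% | 18.4% | 1.43 | 22% |
| 20% | 24.5% | 16.7% | 5.66 | 66% |
| 50% | 30.4% | 11.1% | 34.78 | over 99% |

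**Range for medication.** Over a = 5, 10, 20, 30%, c = 20, 40% and t = 10, 20, 30, 50%, the minimum is 10.0% (a = 5%, c = 40%, t = 10%) and the maximum is over 99.9%. Simulation (40,000 runs per scenario) gives a minimum of 10.5%.

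**Wider check.** A separate simulation applied the SAP's test rule (1,500 runs per scenario) and let use at enrolment reach 60%. At n = 600 the rejection rate was 6–55% with 10% of AEs treated, 18–99.9% with 25% and 62–100% with 50%. At n = 300 the ranges were 5–34%, 11–94% and 33–100%.

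**Therapy.** With c = 5 or 10%, t = 2, 5 or 10%, the same AE risks and the SAP's Fisher rule (4,000 runs per scenario), the rate was 5.9–96.2%.

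**With the flag limited to use at enrolment (t = 0).** The simulated rate at n = 600 was 4.6–5.2% for medication (4.2–5.5% in the wider check) and 2.7–5.5% for therapy.

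**The case against.** **The flag's content is inferred.** No SAP sentence says that it includes later treatment, and a programmer following the baseline label could use the start dates to count only use at enrolment. But the only written definition, to which the protocol's own variables table refers, includes later starts, and nothing in either document restricts it. If use at enrolment is what is meant, one sentence settles it.

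**The size depends on chosen inputs.** This stands. With 60% use at enrolment, 5% AE risk and 10% of AEs treated, the formula gives 7.2%. At n = 300 the 22% and 66% in the table fall to 13.5% and 39%. With only 5% of AEs treated, 40% use and n = 600, the rate is 6–10.5%. The model also leaves out drugs started after enrolment for other reasons, which would dilute the bias. These points lower the bottom of the range but change neither the mechanism nor its direction.

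**It is not strictly a type I error.** The all-use flag really is associated with AEs when AEs are treated. That is fair: the fault is reverse causation presented as a baseline comparison.

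**The study is descriptive.** Protocol 7.7.2 rules out hypothesis testing, SAP section 4 is marked not applicable, and no decision rule uses these tables. This limits the harm, but the SAP still prescribes the tests and a significance level. Treating medication for AEs as its own safety parameter does not remove it from the flag.

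**Conclusion.** The concern holds. Followed as written, the plan lets the outcome help define the groups for concomitant medication and therapy, and then tests the difference as if the groups were fixed at baseline. The chance of a significant result without any association at enrolment runs from little above 5%, when few AEs are treated or use at enrolment is common, to near certainty when about half are treated. All of this rests on assumed AE risk, baseline use and treated share, mostly at n = 600. The direction, towards more AEs among users, does not depend on those values. The change should be made, but its weight is moderate: it protects the interpretation of exploratory subgroup tables in the re-examination report. The injection-count point is correct in principle and secondary.

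**What to change.** In SAP 8.2.1.1 and 8.2.1.3:

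- Define concomitant medication and concomitant therapy, for the tested splits, as those with a start date on or before the first Sayana injection. For starts on the same day, count only those whose recorded purpose is not treatment of an AE.
- State how a record with an incomplete start date is classed, since SAP section 7 allows no imputation.
- Report drugs given for AEs only as the separate safety parameter in Protocol 7.7.1.2.
- If an all-use Yes/No table is wanted, keep it without a test.
- Show AEs by total number of injections without a test, or as AEs per injection interval or per person-time.

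The cost is SAP wording and a filter on start date and purpose, both already on the case report form. It needs slightly more programming and no new data. The downside is that medication started after the first injection for reasons other than an AE no longer counts in the tested split.

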8.2.1.4 Adverse Events by Preferred Terms (AEs/ADRs/SAEs)

All AEs recorded in CRFs will be classified into the system organ class (SOC) and the terms of AE will be coded according to the classification of AEs in 'Precautions of Use' in the local product document of Sayana®/WHO-ART/MedDRA order. All AEs, except for those with causality of adverse event to the study drug classified as 'Unlikely', will be considered as AEs whose causal relationship to the study drug cannot be excluded (hereinafter "Adverse Drug Reaction (ADR)").

- The number and percentage of AE will be presented overall and by preferred term. This will be repeated by:

PFIZER CONFIDENTIAL

- severity
- action
- seriousness
- outcome
- causal relationship to Sayana®
- other causal relationship regarding occurred AE

- The number of subjects and the number of unexpected AE/ADR, SAE/Serious ADR (SADR), unexpected SAE/SADR, AE/ADR will be calculated according to the preferred terms. Also, the proportion of subjects to whom AE occurred will be estimated. In re-examination report, SAE/SADR and unexpected AE/unexpected ADR in accordance with preferred terms will be presented respectively according to the frequency categories of adverse events in the approved local label.
- The subjects with Serious AE, Unexpected AE, Unexpected Serious AE, AE of G eriatric, kidney disorder, liver disorder will be listed for safety analyses sets.
- For subjects excluded from the safety analysis set*, the number of subjects and the number of unexpected AE/ADR, SAE/Serious ADR (SADR), unexpected SAE/SADR, AE/ADR will be calculated according to the preferred terms. Also, the proportion of subjects to whom AE occurred will be estimated.

* Subjects excluded from safety analysis set: Subjects excluded from safety analysis set except for 'subjects who didn't receive Sayana®' and 'subjects for whom adverse event status (Adverse Events status is unknown or missing) could not be established'.

Note: Unexpected AEs/ADRs will be classified by medical review and with reference to the local product document. Terms already included in the local product document are classified as 'expected'. All other terms that are not included in the local product document will be classified as 'unexpected'. These can't be classified without the local product document.

- For subjects excluded from safety analysis set, Serious AE, unexpected AE, Unex pected Serious AE will be listed.

In addition to the above summaries and analyses the following Basic Results tables will also be produced for the final study report:

- Demographic Characteristics in safety analysis set
- Summary of Demographic Characteristics in safety analysis set
- All Adverse Events in safety analysis set
- Summary of Each SOC/PT of Adverse Events in safety analysis set
- Summary of Effectiveness Evaluation in effectiveness analysis set
- Subjects Flow Chart(the number of subjects who started the study, the number of subjects who completed the study)

8.2.2 Efficacy Analysis

The cumulative percent of patients who become pregnant by month 6 will be calculated as $100*(1 - \text{Kaplan-Meier curve at month 6})$, where the Kaplan-Meier (KM) method for estimating survival function will be applied to time-to-pregnancy. Patients who did not become pregnant will be censored at the time of their last follow-up. The KM method will also be used to calculate a 95% confidence interval for this cumulative percent at month 6.

[figure not shown]
[figure not shown]
The rate of pregnancies per 100 person-years of follow-up will be summarized by a 95% confidence interval.

For the rate of pregnancies per 100 person-years of follow-up defined as major events, incidence rate will be calculated as follows:

$100 \times (\text{total number of patients with effectiveness endpoint}) / (\text{total person-years of patients included in the effectiveness analysis set})$ where total person-years is equal to (last evaluation date of outcome - first date of administration +1)/365.25 for all patients in the effective analysis set

The difference between the visual analogue scale (VAS) endometriosis pain scores measured at each visit and the measurement taken before the administration of Sayana[®] will be analyzed using paired t-test.

PFIZER CONFIDENTIAL

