#### 5. RATIONALE AND BACKGROUND

In light of the number of unplanned pregnancies, women recognize the need for contraception and family planning. In addition to controlling the size of their families, couples also want to control the timing and spacing of births. Moreover, the job of family planning will never be finished. With each new generation, comes a new set of parameters affecting use of contraception.

Barriers to using contraception include worries about side effects, health concerns, social disapproval or partner's opposition, financial limitations and lack physical access. In addition, lack of information about nondaily hormonal contraceptives may also be a barrier for women considering contraception. The success of many family planning programs has been linked to removing administrative and medical barriers. Nondaily contraceptives can increase compliance. With oral contraceptives, missed pills are common and contribute to unintended pregnancies. Nondaily contraceptives offer dosing options that reduce the likelihood of missed dose.

Sayana®, revised formulation of depot medroxyprogesterone acetate (DMPA), is specifically formulated for subcutaneous administration. The contraceptive efficacy of Sayana® has been demonstrated in 2 large, multinational contraceptive trials, in which

Sayana® was highly effective and generally well tolerated. Zero pregnancies were reported in both trials (N=1,787) under perfect use conditions.

In addition to its high efficacy, Sayana® delivers a lower dose of medroxyprogesterone acetate than Depo-Provera Contraceptive Injection 150 mg/mL (medroxyprogesterone acetate injectable suspension, 150 mg/mL) and offers subcutaneous administration once every 3 months, thereby eliminating the need for the discipline of daily dosing.

Sayana® benefits from the established clinical history of Depo-Provera CI 150 mg for intramuscular administration, which contains the same active ingredient in a different formulation. Depo-Provera CI 150 mg has been available worldwide for decades and in the United States since 1992. Over 68 million women in over 114 countries worldwide have used Depo-Provera CI 150 mg, and the years of experience with Depo-Provera CI 150 mg worldwide provide a large body of long-term data regarding its safety and efficacy.

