## 7. RESEARCH METHODS

### 7.1. Study design

This study is an open-label, non-comparative, observational, non-interventional, prospective and multi-center study in which subjects administered Sayana® (administered as part of routine practice in Korean health care centers by accredited physicians) will be observed prospectively for a period of 6 months from the enrollment date. The visit schedule or interval will be decided by the investigator.

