### 7.2. Setting

Subjects will be enrolled by continuous registration method. The investigators will assess all the subjects in their practice who receive at least 1 dose of Sayana® 104mg/0.65mL agreed to participate in this study by signing the 'data privacy statement'. All subjects enrolled should meet the usual prescribing criteria for as Sayana® per the local product document and should be entered into the study at the investigator's discretion.

A written, Pfizer and institutional review board (IRB)/independent ethics committee (IEC)-approved, informed consent (ie, Data privacy statement) must be obtained before initiating study procedures.

The eligibility of the subject will be evaluated. After inclusion of the subject and after obtaining written informed consent (ie, Data privacy statement) (prior to any procedure being performed) from the subject or subject's parents/ legal representative (as appropriate), the investigator or site staff will record the subject data into source documents and into a Case Report Form (CRF). Enrollment visit is the visit when subject signs on informed consent (ie, Data privacy statement). Following the baseline data collection , the visits are at the discretion of the investigator and may follow the local usual standard of care, however, the sponsor recommends safety and treatment data

assessments at 3 month intervals (every 12~14weeks) at a minimum during the 6 months of participation. A Follow-up Call is to be conducted by investigator or delegated staffs at least 28 calendar days after the last administration of the study drug within the observational period in order to collect information on the occurrence of adverse events and concomitant medications.

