#### **7.7.2.2. Effectiveness Analyses**

- The cumulative percent of patients who become pregnant by month 6 will be calculated as  $100*(1 - \text{Kaplan-Meier curve at month 6})$ , where the Kaplan-Meier (KM) method for estimating survival function will be applied to time-to-pregnancy. Patients who did not become pregnant will be censored at the time of their last follow-up. The KM method will also be used to calculate a 95% confidence interval for this cumulative percent at month 6.
- The rate of pregnancies per 100 person-years of follow-up will be accompanied by an 95% confidence interval; this confidence interval will be based on the Poisson distribution.
- Mean change in VAS scores from baseline will be tested against zero change using the paired t-test; p-values  $\leq 0.05$  will indicate statistically significant change. Mean change will also be described using a 95% confidence interval.

Detailed methodology for summary and statistical analyses of data collected in this study will be documented in a SAP, which will be dated, filed and maintained by the sponsor. The SAP may modify the plans outlined in the protocol; any major modifications of primary endpoint definitions or their analyses would be reflected in a protocol amendment.

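### If no pregnancy is observed, the planned Kaplan-Meier 95% interval for the month-6 pregnancy percentage is 0% to 0% or undefined, and the companion rate interval is only a partial fallback

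*SAP*

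**What the plan says.** Protocol 7.7.2.2 and SAP 8.2.2 estimate the month-6 pregnancy percentage as 100 times one minus the Kaplan-Meier (KM) curve. On censoring, the SAP says: "Patients who did not become pregnant will be censored at the time of their last follow-up". On precision it says: "The KM method will also be used to calculate a 95% confidence interval for this cumulative percent at month 6". The protocol has the same two sentences. Neither document names a variance formula, a transformation, an exact method or a rule for zero events. The missing-data text, the general methods in SAP 8.1 and the notes in SAP 9.1 do not fill the gap.

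A pregnancy rate per 100 person-years accompanies the percentage. For its interval the protocol says "this confidence interval will be based on the Poisson distribution". The SAP says only: "The rate of pregnancies per 100 person-years of follow-up will be summarized by a 95% confidence interval". The SAP's denominator is the "total person-years of patients included in the effectiveness analysis set". Under SAP 5.2 that set contains women treated for endometriosis pain as well as contraception users.

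The only pregnancy count in either document is in Protocol 5, repeated in SAP 2: "Zero pregnancies were reported in both trials (N=1,787) under perfect use conditions".

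**The concern.** A KM interval gets its width from observed events. If there are none, the planned calculation returns an interval of no width, or no interval at all, for the first-listed effectiveness endpoint. The output would look the same for 10 women as for 600. It would say nothing about the 6-month risk still compatible with the data, which is what a reader wants to know when no pregnancies are reported. The background makes this case foreseeable. SAP 3 also applies the plan to interim analyses and does not reserve the pregnancy analysis for the final report; earlier data cuts hold fewer women, so zero is likelier there.

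The rate interval could supply the missing bound, but as written it is not certain to do so.

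**Working it through.** The plan states no figure for this interval, so there is nothing to reproduce.

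**Inputs.** From the documents: a KM-based 95% interval (Protocol 7.7.2.2, SAP 8.2.2); at least 600 subjects over both indications (Protocol 7.5); 6 months of observation (Protocol 7.1). Assumed: the number of contraception users and the true 6-month risk, neither of which is given.

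**1. KM interval at zero events.** Let d be the pregnancies and n the number at risk at each event time.
- S(6) = product of (1 − d/n) = 1.
- Greenwood variance = S² × sum of d/[n(n − d)] = 0, under any censoring pattern.
- Linear: 0 ± 1.96 × 0, so 0% to 0%. Log: also 0% to 0%. Log-log: needs log(−log 1) = log 0, so undefined.

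With one pregnancy among 600, all followed to month 6, the log-log interval exists: 0.17% (0.02% to 1.18%). The failure is specific to zero.

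**2. Chance of zero pregnancies.** P(0) = (1 − p)^n, with all n users followed to month 6:

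| 6-month risk p | n = 600 | n = 300 |
|---|---|---|
| 0.1% | 55% | 74% |
| 0.2% | 30% | 55% |
| 0.5% | 5% | 22% |
| 1% | 0.2% | 4.9% |

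**3. Rate interval at zero events.** A Wald-type Poisson interval, d ± 1.96 × √d, also has no width at d = 0. The exact two-sided 95% upper limit is −ln(0.025) = 3.689 events, divided by person-years (PY). For 600 women followed 0.5 year each (300 PY):
- on all 300 PY: 3.689/300 = 1.23 per 100 PY;
- if 75% are contraception users (225 PY): 3.689/225 = 1.64;
- if 50% are (150 PY): 3.689/150 = 2.46.

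With the SAP's denominator the bound would therefore be 1.23 even if the appropriate value were 2.46.

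**4. Exact limit on the percentage scale.** With Y contraception users still at risk at month 6, the zero-event limit is 100 × [1 − 0.025^(1/Y)]: 0.61% at Y = 600, 1.22% at 300, 3.6% at 100, 11.6% at 30.

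**5. How large Y might be.** Protocol 7.1 says: "The visit schedule or interval will be decided by the investigator". Protocol 7.2 only recommends "assessments at 3 month intervals (every 12~14weeks) at a minimum during the 6 months of participation". Two 12-week intervals end at day 168, before about day 183 (365.25/2). If every last evaluation fell on day 168, Y would be 0 at day 183 and the limit in step 4 would not exist. The rate bound would still work: by the SAP's day count, 600 × 169/365.25 = 277.6 PY, and 3.689/277.6 = 1.33 per 100 PY; with 300 users, 138.8 PY and 2.66.

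**The case against.** The strongest reply is that little depends on this interval. Protocol 7.7.2 calls the analyses primarily descriptive with no hypotheses tested, SAP 4 has no decision rules, and Protocol 6 mentions effectiveness only as other information. No estimate is biased. A 0% to 0% interval beside zero pregnancies is visibly degenerate and could be supplemented at reporting. This stands, and it limits the weight.

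Second, the protocol already plans a Poisson interval for the rate, and the SAP's silence does not revoke it. This also stands in part. A reader might infer that the study would have no error bar on pregnancy at all; the documents do not support that. What is missing is exact limits and a denominator restricted to contraception users.

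Third, the percentage-scale limit in step 4 has faults of its own. It discards follow-up before month 6. If last evaluations fell evenly over days 168 to 196, then 13/28 = 46% would reach day 183, so Y would be about 280 of 600 and the limit 1.31%. That is worse than the 1.18% log-log limit for one early pregnancy with all 600 at risk. Evaluations out to day 196 also run past the 6-month window, so 280 may be generous. This is why the rate bound should lead and the percentage limit be optional.

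**Conclusion.** The point holds for zero pregnancies, with minor to moderate weight. In that case the prescribed method gives an interval of no width or none, and no text in either document repairs it. The arithmetic needs no assumption. The likelihood of the case does: it rests on an assumed 6-month risk and number of contraception users, and P(0) runs from 74% to 0.2% over the range shown.

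Three stronger readings are not supported:
- That zero pregnancies should be expected. The 0 of 1,787 comes from perfect use, and no usual-care rate is given.
- That the KM interval is unsound in general, or that a particular transformation must be named. No fault is shown here once a pregnancy is seen.
- That the interval has a further coverage problem. Scoring the degenerate result as a miss lowers computed coverage, but that only restates P(0).

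**What to change.** In SAP 8.2.2:

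1. Keep the KM estimate. State that if no pregnancy is observed, the KM interval is replaced by an exact upper limit.
2. Compute the rate interval with exact Poisson limits on contraception users' person-years only, and make it the main zero-event bound (3.689 divided by PY: 1.23 per 100 PY on 300 PY, 2.46 on 150 PY).
3. Optionally, also report 100 × [1 − 0.025^(1/Y)], giving Y and the day that defines month 6 (0.61% at Y = 600, 1.22% at Y = 300). Describe it as conservative under censoring and uninformative if Y is small. A beta product interval at all event counts is an acceptable alternative.

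The cost is a few sentences in the SAP and a few lines of code, with no new data. The downside is that a zero-pregnancy result carries a wider interval. Restricting the person-years also raises the rate bound as the share of contraception users falls.
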